6. Subject Population: Provide a detailed description of the types of human subjects who will be recruited into this study.

Subjects will include pregnant patients with a history of opioid use disorder who are compliant in their use medication assisted treatment (methadone, buprenorphine, suboxone) who are scheduled for cesarean delivery or who require a cesarean delivery during labor for non-urgent reasons, including

but not limited to arrest of dilation, arrest of descent, failed trial of labor, non-reassuring fetal heart tracing. As soon as individuals are identified as being eligible (in the clinic, at their pre-operative visit or on admission to the labor floor) they will be provided information on the study. Individuals will not be approached for consent unless they are scheduled for a cesarean delivery or require a non-urgent cesarean delivery out of labor (see inclusion criteria below)

7. Subject classification: Check off all classifications of subjects that will be specifically recruited for enrollment in the research project. Will subjects who may require additional safeguards or other considerations be enrolled in the study? If so, identify the population of subjects requiring special safeguards and provide a justification for their involvement.

 Children	 Healthy	 Fetal material, placenta, or dead fetus
 Non-English Speaking	 Prisoners	 Economically disadvantaged persons
 Decisionally Impaired	 Employees	 Pregnant women and/or fetuses
 Yale Students	 Females of childbearing potential	

NOTE: Is this research proposal designed to enroll children who are wards of the state as potential subjects?

Yes  No

8. Inclusion/Exclusion Criteria: What are the criteria used to determine subject inclusion or exclusion?

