Inclusion: 18 years or older, English-speaking, history of opioid use disorder with current use of MAT during pregnancy, scheduled for cesarean delivery for their current pregnancy for any indication [examples of **elective c-section** (decision made for c-section to be performed prior to onset of labor): fetal malpresentation, suspected macrosomia, prior c-section, abnormal placentation, patient preference], negative toxicology screen upon admission to the hospital for their cesarean section, no prior administration of betamethasone for fetal lung maturity within 24h of their scheduled cesarean delivery or women who require a c-section out of labor for non-urgent reasons and have received information about the study and the consent upon admission to the hospital and therefore have had adequate time to review the consent prior to the delivery ( (Arrest of dilation, Arrest of descent, Failed induction of labor, Patient choice to discontinue trial of labor, Fetal malpresentation with no to minimal dilation (<4cm dilation), planned cesarean delivery at a later date presenting in labor or with rupture of membranes)

- Exclusion: under 18 years old, non-English speaking, screen positive for illicit substance(s) on their admission toxicology screen, require general anesthesia for their cesarean section due to maternal/fetal indication for non-anticipated urgency (thus no longer 'elective') or failure of adequate intra-operative pain control with spinal anesthesia, medical history including known cardiovascular disease, heart failure, uncontrolled hypertension (SBP  $\geq$ 160mmHg and/or DBP  $\geq$ 110mmHg), uncontrolled gestational or pregestational diabetes, active GI bleed or untreated peptic ulcer, untreated infectious diseases including tuberculosis or systemic candida, patients requiring a c-section out of labor for urgent reasons who have not received information about the study and the consent form upon admission to the hospital (Non-reassuring fetal heart rate tracing (persistent category II heart rate tracing), Category III fetal heart rate tracing, Acute placental abruption, Cord prolapse, Fetal malpresentation at advanced (>4cm dilation)).

9. How will eligibility be determined, and by whom?

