Eligibility will be determined by review of the patient electronic medical chart by their obstetrics provider, who will be consenting them for the study, to assess their eligibility given their medical history as well as later determine exclusion laboratory criteria (admission toxicology screen)

10. Risks: Describe the reasonably foreseeable risks, including risks to subject privacy, discomforts, or inconveniences associated with subjects participating in the research.

Risks with single administration dexamethasone are most relevant for special populations that have been excluded from this study, including:

Cardiovascular disease: Heart failure and/or hypertension; use has been associated with fluid retention, electrolyte disturbances, and hypertension. Use with caution following acute MI; corticosteroids have been associated with myocardial rupture.

Diabetes: may alter glucose production/regulation leading to hyperglycemia.

Gastrointestinal disease: (diverticulitis, recent intestinal anastomoses, active or latent peptic ulcer, ulcerative colitis, abscess or other pyogenic infection) due to perforation risk

In regard to subjects who plan to breastfeed following delivery:

- Although the risk to newborns is unknown for any corticosteroid, use of dexamethasone is encouraged by ACOG (the ObGyn national body), and considered safe in pregnancy, especially for short term use. It is routinely given to mothers for fetal benefits, mainly lung maturity for suspected pre-term deliveries/neonates (ACOG Committee Opinion 713: Antenatal Corticosteroids for Fetal Maturity)
- When administered to lactating women, small amounts of corticosteroids entered human milk. Although data on the use of dexamethasone during lactation are not available, the American Academy of Pediatrics classified the corticosteroids prednisone and prednisolone as compatible with breastfeeding(Katz FH and Duncan BR: Entry of prednisone into human milk. *N Engl J Med* 293:1154, 1975. McKenzie SA et al.: Secretion of prednisone into breast milk. *Arch Dis Child* 50:894-6, 1975. Ost L et al.: Prednisolone excretion in human milk. *J Pediatr* 106:1008-11, 1985. Committee on Drugs, American Academy of Pediatrics. The transfer of drugs and other chemicals into human breast milk. *Pediatrics* 108:776-89, 2001.).

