- If you plan to breastfeed your baby, this drug does appear in small quantities in breast milk and thus there is theoretical risk of use of corticosteroids have the potential to cause adverse events in a breastfeeding infant (eg, growth suppression, interfere with endogenous corticosteroid production) with chronic use, although information related to prolonged use is not available. Single doses of dexamethasone are considered compatible with breastfeeding; (WHO 2002).
- No data are available on the transfer of dexamethasone into human milk. It is likely similar to that of prednisone which is extremely low. Doses of prednisone as high as 120 mg fail to produce clinically relevant milk levels (equivalent of 18mg Dexamethasone). This product is commonly used in pediatrics for treating immune syndromes such as arthritis and, particularly, acute onset asthma or other bronchoconstrictive diseases. It is not likely that the amount in milk would produce clinical effect unless used in high doses over prolonged periods(Hale, Thomas W., and Hilary E. Rowe. *Medications and Mothers' Milk* 2017. Springer Publishing Company, 2016.).

- The half-life is 1 to 5 hours, with no drug at high enough levels to remain detectable in breast milk after one day.
- Breastfeeding while on corticosteroids carries minimal risk of exposure to the infant, which may be further decreased by nursing immediately before or more than 4 hours after the dose (Makol, Ashima, Kerry Wright, and Shreyasee Amin. "Rheumatoid Arthritis and Pregnancy." *Drugs* 71.15 (2011): 1973-1987 Ost L, Wettrell G, Bjorkhem I, et al. Prednisolone excretion in human milk. *J Pediatr* 1985 Jun; 106(6): 1008-11.).

Additional risk and reactions listed below are almost exclusively associated with repeated and/or high dose use and some are based on reports for other agents in this same pharmacologic class and may not be specifically reported for dexamethasone. (Frequency not defined):

*Cardiovascular:* Bradycardia, cardiac arrhythmia, cardiac failure, cardiomegaly, circulatory shock, edema, embolism (fat), hypertension, hypertrophic cardiomyopathy (premature infants), myocardial rupture (post-MI), syncope, tachycardia, thromboembolism, thrombophlebitis, vasculitis

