*Central nervous system:* Depression, emotional lability, euphoria, headache, increased intracranial pressure, insomnia, malaise, myasthenia, neuritis, neuropathy, paresthesia, personality changes, pseudotumor cerebri (usually following discontinuation), psychic disorder, seizure, vertigo

*Dermatologic:* Acne vulgaris, allergic dermatitis, alopecia, atrophic striae, diaphoresis, ecchymoses, erythema, facial erythema, fragile skin, hyperpigmentation, hypertrichosis, hypopigmentation, perianal skin irritation (itching, burning, tingling; following IV injection), petechiae, skin atrophy, skin rash, subcutaneous atrophy, suppression of skin test reaction, urticaria, xeroderma

*Endocrine & metabolic:* Adrenal suppression, carbohydrate intolerance, Cushing syndrome, decreased glucose tolerance, decreased serum potassium, diabetes mellitus, fluid retention, glycosuria, growth suppression (children), hirsutism, HPA-axis suppression, hyperglycemia, hypokalemic alkalosis, menstrual disease, moon face, negative nitrogen balance, protein catabolism, redistribution of body fat, sodium retention, weight gain

*Gastrointestinal:* Abdominal distention, gastrointestinal hemorrhage, gastrointestinal perforation, hiccups, increased appetite, nausea, pancreatitis, peptic ulcer, pruritus ani (following IV injection), ulcerative esophagitis

*Genitourinary:* Defective (increased or decreased) spermatogenesis

*Hematologic & oncologic:* Kaposi sarcoma, petechial, tumor lysis syndrome

*Hepatic:* Hepatomegaly, increased serum transaminases

*Hypersensitivity:* Anaphylactoid reaction, anaphylaxis, angioedema, hypersensitivity

*Infection:* Infection, sterile abscess

*Neuromuscular & skeletal:* Amyotrophy, aseptic necrosis of bones (femoral and humeral heads), bone fractures, Charcot-like arthropathy, myasthenia, myopathy (particularly in conjunction with neuromuscular disease or neuromuscular-blocking agents), osteoporosis, rupture of tendon, steroid myopathy, vertebral compression fracture

*Ophthalmic:* Exophthalmos, glaucoma, increased intraocular pressure, subcapsular posterior cataract

*Respiratory:* Pulmonary edema

11. Minimizing Risks: Describe the manner in which the above-mentioned risks will be minimized.

Populations at greatest risk with receipt of single dose IV dexamethasone will be excluded from the study.

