3. The investigation does NOT involve a route of administration or dosage level or use in populations or other factor that significantly increases the risks (or decreases the acceptability of the risks) associated with the use of the drug product Single use (rather than chronic or high-dose use) administration of dexamethasone in our select patient population (excluding patients at higher risk of adverse effects of the medication) at the standard dosage level does not involve a dosage level, route, or population that significantly increases the risk associated with the use of this drug. Please see additional text on breastfeeding information for safety in infants.	
4. The investigation will be conducted in compliance with the requirements for institutional (HIC) review and with the requirements for informed consent of the FDA regulations (21 CFR Part 50 and 21 CFR Part 56).	
5. The investigation will be conducted in compliance with the requirements regarding promotion and charging for investigational drugs.	

**Exempt Category 2** (all items i, ii, and iii must be checked to grant a category 2 exemption)

i. The clinical investigation is for an *in vitro* diagnostic biological product that involves one or more of the following (check all that apply):

- Blood grouping serum
- Reagent red blood cells
- Anti-human globulin

ii. The diagnostic test is intended to be used in a diagnostic procedure that confirms the diagnosis made by another, medically established, diagnostic product or procedure; and

iii. The diagnostic test is shipped in compliance with 21 CFR §312.160.

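### Section I item 10 says women with ulcerative colitis, diverticulitis or a recent bowel anastomosis are excluded for perforation risk, but the item 8 exclusions name none of the three

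*Combined protocol and SAP*

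**What the plan says.** Section I, item 10 (Risks) opens with "Risks with single administration dexamethasone are most relevant for special populations that have been excluded from this study, including" and then describes cardiovascular disease, diabetes and gastrointestinal disease. The gastrointestinal group is spelled out as "diverticulitis, recent intestinal anastomoses, active or latent peptic ulcer, ulcerative colitis, abscess or other pyogenic infection) due to perforation risk".

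Item 8 (Inclusion/Exclusion Criteria) excludes known cardiovascular disease, heart failure and uncontrolled hypertension (systolic at least 160 mmHg and/or diastolic at least 110 mmHg). It continues with "uncontrolled gestational or pregestational diabetes, active GI bleed or untreated peptic ulcer, untreated infectious diseases including tuberculosis or systemic candida". There is no other bowel-disease or bowel-surgery criterion.

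Item 9 says who applies the criteria: "Eligibility will be determined by review of the patient electronic medical chart by their obstetrics provider".

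Two other places rely on the exclusions:

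- Item 11 (Minimizing Risks) consists of one sentence: "Populations at greatest risk with receipt of single dose IV dexamethasone will be excluded from the study".
- Section II, Drugs/Biologics, Exempt Category 1, point 3 justifies the IND exemption by single use "in our select patient population (excluding patients at higher risk of adverse effects of the medication) at the standard dosage level".

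The background text that follows in Section II (item 2) likewise calls single-dose risk minimal in patients who do not have the comorbidities discussed earlier.

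**The concern.** Item 10 describes the listed populations as already excluded, but only item 8 can exclude anyone. If item 8 is applied as written, a woman with quiescent ulcerative colitis or a recent bowel anastomosis meets no named exclusion. She can then be randomised and given dexamethasone, although the protocol has told the IRB that women like her are kept out.

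The trial's results are not at stake. The issue is the safety of a few possible subjects and the accuracy of the risk statement on which approval and the IND exemption rest. It matters more because item 12 says the investigators do not regard the risks of dexamethasone as minimal, and because item 11 offers no other protection.

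**Working it through.** The plan states no figure to reproduce. The check sets the two lists side by side and then sizes the gap under stated assumptions.

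**Step 1: item 10 against item 8.** Item 10 names nine conditions.

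| Condition in item 10 | Coverage in item 8 |
|---|---|
| Heart failure | Covered by name |
| Acute MI | Covered through known cardiovascular disease |
| Hypertension | Only if uncontrolled |
| Diabetes | Only if uncontrolled |
| Peptic ulcer, active or latent | Only if untreated |
| Abscess or other pyogenic infection | Partly, through untreated infectious diseases |
| Diverticulitis | Not named |
| Recent intestinal anastomosis | Not named |
| Ulcerative colitis | Not named |

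Tally: 2 fully covered + 3 covered with a threshold + 1 partly covered + 3 not named = 9.

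**Step 2: could other wording catch the three?** Ulcerative colitis would be caught while it is bleeding, under the active GI bleed criterion, and not otherwise. Untreated diverticulitis would be caught only if a reader classed it as an infectious disease. No listed criterion reaches a recent anastomosis. None of the three appears as an eligibility criterion elsewhere in the protocol.

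**Step 3: does the protocol itself treat these conditions as a single-dose risk?** Later in item 10 it says "Additional risk and reactions listed below are almost exclusively associated with repeated and/or high dose use", and the list that follows includes gastrointestinal perforation. That lowers the absolute risk. The qualifier, however, applies to the reactions listed after it. The perforation statement for these bowel conditions stands before it, under a sentence about single administration, so the protocol singles these women out.

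**Step 4: how many women might be affected?** The target of 40 subjects comes from Section III, item 1. The documents give no prevalence, so let p be the assumed share of eligible women with at least one of the three conditions, from 0.1% to 2%. The allocation ratio is not stated either; 1:1 is assumed, giving 20 women on dexamethasone.

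- Expected number among 40 = 40p
- Chance of at least one among 40 = 1 − (1 − p)^40
- Expected number among 20 dosed = 20p
- Chance of at least one among 20 dosed = 1 − (1 − p)^20

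| p | Expected of 40 | At least one of 40 | Expected of 20 dosed | At least one of 20 dosed |
|---|---|---|---|---|
| 0.1% | 0.04 | 3.9% | 0.02 | 2.0% |
| 0.5% | 0.2 | 18.2% | 0.1 | 9.5% |
| 1% | 0.4 | 33.1% | 0.2 | 18.2% |
| 2% | 0.8 | 55.4% | 0.4 | 33.2% |

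Across the range the chance that nobody with these conditions is dosed is at least 66.8% (100% − 33.2%), so zero is the most likely count.

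**The case against.** The mismatch in wording cannot be disputed; the argument is over how much it matters.

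- **The list is open.** Item 8 introduces its medical exclusions with the word *including*, item 9 leaves the chart review to an obstetrics provider, and item 11 states the general intent. A provider reading items 8 to 11 together has grounds to exclude all three conditions. That is fair, but it permits exclusion without requiring it. For unscheduled cesareans, possibly overnight, Section III has an investigator check the chart against the listed criteria before phone consent, and that check needs an explicit rule.
- **There are other safeguards.** Dosing is by weight, nurses assess the women routinely during the stay, and adverse events are reviewed after every subject. These limit or detect harm; they do not keep a high-risk woman from being dosed.
- **The probabilities rest on an assumed prevalence.** This stands. The upper figures, 55% and 33%, follow from the 2% bound, which nothing in the documents supports. The conclusion rests on the text and not on these figures.
- **Item 10 may be too broad.** Item 8 repeatedly uses activity limits such as *uncontrolled* and *untreated*, so the investigators may have meant a narrower group. For ulcer, hypertension and diabetes this is plausible, and either item could change. For the three unnamed conditions item 8 has no corresponding entry to act as a threshold. Narrowing item 10 instead would mean justifying dosing these women and revisiting the statements in item 11 and Section II.
- **Unqualified terms could exclude women with past or quiescent disease.** This also stands, as a small recruitment cost.

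**Conclusion.** The concern holds. Of the nine conditions item 10 describes as excluded, three have no counterpart in item 8, and item 11 and the Section II exemption answer both depend on that exclusion. The protocol therefore states a safeguard that its working criteria do not contain.

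The practical size is small. Assuming 0.1% to 2% combined prevalence and 1:1 allocation, 0.02 to 0.4 women with one of these conditions would be expected to receive dexamethasone. Absolute risk from one dose is probably low, and no endpoint, power or analysis figure is touched. The text comparison needs no assumption; only the sizing does. This should be corrected because the possible harm is serious and the correction is cheap.

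**What to change.** **Item 8:** add ulcerative colitis, diverticulitis, recent intestinal anastomosis, and active abscess or other pyogenic infection to the exclusions. It would help the chart reviewer to state what counts as recent and whether past or quiescent disease is meant.

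**Peptic ulcer, hypertension and diabetes:** make items 8 and 10 agree, in either direction. Widen item 8 (for ulcer, to include latent disease) or, if *untreated* and *uncontrolled* are the intended limits, use those words in item 10.

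**Cost:** one protocol amendment and a few lines on the eligibility check. No new procedure is needed, because eligibility is already decided by chart review of medical history. A few women, possibly none, become ineligible in a 40-subject trial that plans 5 to 5.5 years of data collection.

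**Optional tidying in the same amendment:** item 6 counts a non-reassuring fetal heart tracing among its non-urgent examples ("but not limited to arrest of dilation, arrest of descent, failed trial of labor, non-reassuring fetal heart tracing"), while item 8 lists it as urgent. Deleting it from item 6 removes the conflict. Who is enrolled does not change, since it is not among item 8's six listed non-urgent reasons for cesarean out of labor. The conclusion above does not depend on this point.

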### **Greater Than Minimal Risk DSMP (subjects receiving study drug, Dexamethasone)**

#### **1. Personnel responsible for the safety review and its frequency:**

The principal investigator will be responsible for monitoring the data, assuring protocol compliance, and conducting the safety reviews at the specified frequency, which must be conducted at a minimum of every 6 months (including when reapproval of the protocol is sought). During the review process, the principal investigator (monitor) will evaluate whether the study should continue unchanged, require modification/amendment, or close to enrollment. The principal investigator, the Institutional Review Board (IRB) or Yale Cancer Center Data and Safety Monitoring Committee (DSMC) have the authority to stop or suspend the study or require modifications.

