12. Data and Safety Monitoring Plan: Include an appropriate Data and Safety Monitoring Plan (DSMP) based on the investigator's risk assessment stated below. (Note: the HIC will make the final determination of the risk to subjects.)

- a. What is the investigator's assessment of the overall risk level for subjects participating in this study? minimal risk in pregnant women and fetuses (when no drug is taken), greater than minimal risk in non-pregnant subjects when taking drug
- b. If children are involved, what is the investigator's assessment of the overall risk level for the children participating in this study? As only data collection from the medical record will be performed on the infants there is minimal risk to infants participating in the study

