**6. Plan for reporting UPIRSOs (including Adverse Events) to the IRB**

The principal investigator will report the following types of events to the IRB:

Any incident, experience or outcome that meets ALL 3 of the following criteria:

- 1. Is unexpected (in terms of nature, specificity, severity, or frequency) given (a) the research procedures described in the protocol-related documents, such as the IRB-approved protocol and informed consent document and (b) the characteristics of the subject population being studied; AND

2. Is related or possibly related to participation in the research (*possibly related* means there is a reasonable possibility that the incident, experience, or outcome may have been caused by the procedures involved in the research); AND
3. Suggests that the research places subjects or others at greater risk of harm (including physical, psychological, economic, legal, or social harm) than was previously known or recognized.

Unanticipated Problems Involving Risks to Subjects or Others (UPIRSOs) may be medical or non-medical in nature, and include – but are not limited to – *serious, unexpected, and related adverse events* and *unanticipated adverse device effects*. **Please note** that adverse events are reportable to the IRB as UPIRSOs **only** if they meet all 3 criteria listed above.

These UPIRSOs/SAEs will be reported to the IRB in accordance with IRB Policy 710, using the appropriate forms found on the website. All related events involving risk but not meeting the *prompt* reporting requirements described in IRB Policy 710 should be reported to the IRB in summary form at the time of continuing review. If appropriate, such summary may be a simple brief statement that events have occurred at the expected frequency and level of severity as previously documented. In lieu of a summary of external events, a current DSMB report can be submitted for research studies that are subject to oversight by a DSMB (or other monitoring entity that is monitoring the study on behalf of an industry sponsor).

**7. Plan for reporting adverse events to co-investigators on the study, as appropriate the protocol's research monitor(s), e.g., industrial sponsor, Yale Cancer Center Data and Safety Monitoring Committee (DSMC), Protocol Review Committee (PRC), DSMBs, study sponsors, funding and regulatory agencies, and regulatory and decision-making bodies.**

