**Minimal risk for infants and subjects receiving placebo**

The principal investigator is responsible for monitoring the data, assuring protocol compliance, and conducting the safety reviews at the specified frequency [monthly]. During the review process the principal investigator will evaluate whether the study should continue unchanged, require

modification/amendment, or close to enrollment. The principal investigator, the Institutional Review Board (IRB) or Yale Cancer Center Data and Safety Monitoring Committee (DSMC) have the authority to stop or suspend the study or require modifications.

This protocol presents minimal risks to the subjects (receiving placebo and infants of all subjects) and Unanticipated Problems Involving Risks to Subjects or Others (UPIRSOs), including adverse events, are not anticipated. In the unlikely event that such events occur, Reportable Events (which are events that are serious or life-threatening and unanticipated (or anticipated but occurring with a greater frequency than expected) and possibly, probably, or definitely related) or Unanticipated Problems Involving Risks to Subjects or Others that may require a temporary or permanent interruption of study activities will be reported immediately (if possible), followed by a written report within 5 calendar days of the Principal Investigator becoming aware of the event to the IRB (using the appropriate forms from the website) and any appropriate funding and regulatory agencies. The investigator will apprise fellow investigators and study personnel of all UPIRSOs and adverse events that occur during the conduct of this research project via email as they are reviewed by the principal investigator. The protocol's research monitor: Yale Cancer Center Data and Safety Monitoring Committee (DSMC), will be informed of adverse maternal events within 5 days of the event becoming known to the principal investigator.

c. For multi-site studies for which the Yale PI serves as the lead investigator: n/a

- i. How will adverse events and unanticipated problems involving risks to subjects or others be reported, reviewed and managed? Write here
- ii. What provisions are in place for management of interim results? Write here
- iii. What will the multi-site process be for protocol modifications? Write here

13. Statistical Considerations: Describe the statistical analyses that support the study design.

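### Item 12 heads its two maternal safety plans by treatment received, so following them as headed needs the allocation in a double-blind trial and gives the dexamethasone arm the longer guaranteed review interval

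*Combined protocol and SAP*

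**What the plan says.** Section I, item 4 (Research Plan) describes a double-blind, placebo-controlled randomised trial in 40 women. Item 12 (Data and Safety Monitoring Plan) then deals with safety in three places.

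- **Item 12a, overall risk level.** The rating is "minimal risk in pregnant women and fetuses (when no drug is taken), greater than minimal risk in non-pregnant subjects when taking drug".
- **First plan.** It is headed "Greater Than Minimal Risk DSMP (subjects receiving study drug, Dexamethasone)" and has seven numbered subsections. Subsection 1 gives the safety reviews to the principal investigator, "which must be conducted at a minimum of every 6 months". Subsection 3 has the principal investigator and named colleagues attribute adverse events. Subsection 6 defines reportable events by three criteria that must all be met, and says: "These UPIRSOs/SAEs will be reported to the IRB in accordance with IRB Policy 710, using the appropriate forms found on the website."
- **Second plan.** It is headed "Minimal risk for infants and subjects receiving placebo", and the body repeats the split: "This protocol presents minimal risks to the subjects (receiving placebo and infants of all subjects)". The principal investigator is again responsible for "conducting the safety reviews at the specified frequency [monthly]". Reportable events are defined differently and are notified at once if possible, "followed by a written report within 5 calendar days of the Principal Investigator becoming aware of the event to the IRB".

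Item 12 names no unblinded monitor and gives no way to place a woman under one plan or the other without her allocation.

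**The concern.** The two headings sort women by what they received, and a blinded investigator does not know that. The person who must choose the review interval and the IRB reporting rule also judges whether each event is related to treatment. Relatedness is a subjective grade, and knowing the arm can shift it. If the headings were followed, the safety comparison would lose the protection that blinding is meant to give.

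The direction is also the reverse of what one would expect. Subsection 2 of the first plan says the risks of dexamethasone are not regarded as minimal, yet its scheduled reviews may be six months apart while the placebo plan's are monthly. What is at stake is safety oversight and even-handed attribution of adverse events. The pain and opioid comparisons in item 13 are largely unaffected, and sample size and alpha are untouched.

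**Working it through.** **The two plans as headed**

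| | First plan (dexamethasone) | Second plan (placebo, and infants of all subjects) |
|---|---|---|
| Reviewer | Principal investigator | Principal investigator |
| Scheduled review | At least every 6 months | Monthly |
| Reportable event | Unexpected, at least possibly related, and suggesting greater risk than known | Serious or life-threatening, unanticipated or more frequent than expected, and at least possibly related; or a problem that may interrupt the study |
| IRB timing | Per Policy 710 (deadlines not given in the documents) | Written report within 5 calendar days |

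**Scheduled reviews guaranteed.** Item 2 gives 5 to 5.5 years of data collection, which is 60 to 66 months. Reviews = months / interval.

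- First plan: 60/6 = 10 to 66/6 = 11, as a minimum.
- Second plan: 60/1 = 60 to 66/1 = 66.
- Ratio: 60/10 = 66/11 = 6.

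**Women enrolled between six-monthly reviews.** Section III targets 40 women. Even accrual over the collection period and 1:1 allocation are assumptions; the documents state neither.

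- Enrolment per month: 40/66 = 0.61 to 40/60 = 0.67.
- Per 6 months: 6 × 40/66 = 3.6 to 6 × 40/60 = 4.0 women.
- On dexamethasone: half of these, 1.8 to 2.0 women.

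**The review at completion.** Subsection 7 of the first plan adds a review of all adverse events as every subject completes. Over 40 women that is one every 60/40 = 1.5 to 66/40 = 1.65 months on average. If completion means discharge, each woman is reviewed within days of surgery, since item 13 gives a stay of 2 to 4 days. If it means the optional 12-month call in item 4, the review comes far later. The text does not define completion.

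**Can both plans be met without the code?** Yes, for the intervals. Six months is a minimum, so one monthly review over all women satisfies both, and dexamethasone women are then covered by 60 to 66 scheduled reviews. For IRB reporting, a blinded investigator would have to apply both rules to every woman. The protocol gives neither instruction.

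**The case against.** The best defence is that the headings are loose and the working text already treats the women as one group. Both plans describe a study-level decision by the same person: whether to continue, change or close enrolment. Subsection 2 rates the study as a whole as above minimal risk. Subsections 3, 4 and 7 cover each subject, events during the study, and every completing subject. In the second plan, the 5-day notice to the monitoring committee is worded for maternal events generally. Item 12a is ambiguous: study drug is given after delivery, so its wording can mean before versus after birth and not placebo versus dexamethasone. All of this stands, and it points to a pooled blinded review as the likely practice.

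It does not remove the point. The arm labels appear in both headings and again in the second plan's body, and subsections 3, 4 and 7 sit under the dexamethasone heading. The protocol never resolves the conflict.

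A reader might infer four stronger things, none of which the documents support:

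- **That the investigator will be unblinded.** A monthly review of everyone needs no code.
- **That adverse events will be collected or handled differently by arm.** No arm-specific collection is described, and attribution and grading are worded for all.
- **That dexamethasone events reach the IRB later or under a weaker rule.** Policy 710's deadlines are not given and the two event definitions overlap, so neither rule can be called stricter.
- **That dexamethasone women will get only 10 to 11 reviews.** That is a floor, and the completion review adds to it.

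**Conclusion.** The point holds as a fault in the stated rule: item 12 assigns women to monitoring plans by a variable that the blinded investigator should not have, and the guaranteed scheduled interval is longer in the arm rated at greater risk. The size is 6 months against 1 month, or at least 10 to 11 scheduled reviews against 60 to 66. This is the maximum gap, because the plan permits more frequent review and adds one at each completion. Those counts rest only on the stated collection period; the figure of 1.8 to 2.0 dexamethasone women per six months also assumes even accrual and 1:1 allocation. No event rate is assumed, and no actual unblinding or unequal handling is shown. It should be corrected because a safety plan is judged by what it guarantees, and a blinded investigator should be able to follow this one as written.

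**What to change.** Merge the maternal monitoring into one plan through these edits to item 12:

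- Re-head the first plan for all randomised women.
- Set its scheduled review to monthly, plus a review as each woman is discharged, which also settles what completion means.
- Apply one IRB reporting rule to both arms. Subsection 6's definition can stay as it is; add the 5-calendar-day written report, without displacing any shorter deadline in Policy 710.
- Move the 5-day committee notice for maternal events into this plan.
- State that the investigators who review and attribute events stay blinded, with emergency unblinding when needed to treat a woman. Allow by-arm review by the monitoring committee if it asks, so that its authority to stop the study is not weakened.
- In item 12a, give all randomised women one risk level, greater than minimal, in line with subsection 2.
- Limit the minimal-risk paragraph to infants.

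Suggested core wording: *All randomised women are monitored under this plan. The investigators who review and attribute adverse events remain blinded to assignment. Safety is reviewed monthly and when each woman is discharged. The same IRB reporting rule applies in both arms.*

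The cost is a small IRB modification. The second plan already requires monthly reviews and covers the infants of all subjects, so no meetings are added. At 0.61 to 0.67 enrolments a month, the extra review work is slight.
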